C4671005 (NCT04960202), a Phase 2/3, randomized, double-blind, placebo-controlled study in nonhospitalized symptomatic adult participants with a laboratory-confirmed diagnosis of SARS-CoV-2 infection, included participants 18 years of age and older with at least 1 risk factor for progression to severe disease and with a COVID-19 symptom onset of ≤ 5 days. The study excluded individuals with a history of prior COVID-19 infection or SARS-CoV-2 vaccination before the Day 34 visit. The primary efficacy endpoint was the proportion of participants with COVID-19 related hospitalization or death from any cause through Day 28.

In the analysis of the primary endpoint from all participants enrolled in Study C4671005, an 89% reduction in COVID-19-related hospitalization or death from any cause compared with placebo in participants treated within 3 days of symptom onset was observed. 0.7% of participants who received PF-07321332/ritonavir were hospitalized through Day 28 following randomization (5 of 697 hospitalized with no deaths), compared to 6.5% of participants who received placebo and were hospitalized or died (44 of 682 hospitalized with 9 subsequent deaths) ($p < 0.0001$). In a secondary endpoint, PF-07321332/ritonavir reduced the risk of hospitalization or death for any cause by 88% compared with placebo in participants treated within 5 days of symptom onset; 0.8% of patients who received PF-07321332/ritonavir were hospitalized or died through Day 28 following randomization (8 of 1039 hospitalized with no deaths) compared with 6.3% of patients who received placebo (66 of 1046 hospitalized with 12 subsequent deaths) ($p < 0.0001$). Treatment with PF-07321332/ritonavir was safe and well tolerated.

A prespecified interim analysis of Study C4671002, which included 45% of the trial's planned enrollment, showed that the novel primary endpoint of self-reported, sustained alleviation of all symptoms for 4 consecutive days, as compared to placebo, was not met. The key secondary endpoint of COVID-19-related hospitalization or death from any cause through Day 28 was also examined at the interim analysis, showing 0.6% of those who received PF-07321332/ritonavir were hospitalized following randomization (2 of 333 hospitalized with no deaths), compared to 2.4% of participants who received placebo and were hospitalized (8 of 329 hospitalized with no deaths).

This study, C4671002, is ongoing and participant-level treatment assignment remains blinded.

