9.5. Sample Size Determination

The initial estimate of required sample size was based on the primary endpoint, the difference in time to sustained alleviation of all targeted COVID-19 associated signs/symptoms between participants who were treated ≤ 3 days after COVID-19 symptom onset, treated with PF-07321332/ritonavir compared to placebo. The sample size was calculated based on a 2-sample test-parallel design–log-rank test, assuming a 90% power, 2-sided test at $\alpha = 0.05$, approximate accrual rate of 30 participants per day, 2 days difference in the median days to sustained alleviation of all targeted COVID-19-associated symptoms (6 days for PF-07321332/ritonavir and 8 days for placebo ie, a 25% reduction in time to sustained alleviation of all targeted COVID-19 signs/symptoms) based on the Lilly-BLAZE-1¹ and assuming a 18% study discontinuation rate, the sample size of approximately 800 participants (approximately 515 events) will provide 90% power to detect that difference. Allowing for approximately 30% of participants with COVID-19 symptom onset > 3 days, a sample size of approximately 1140 participants were to be enrolled for this study.

After the second interim analysis (80% planned enrollment through Protocol Amendment 4), in order to improve estimation precision of the treatment effect in the clinically relevant key secondary endpoint of COVID-19-related hospitalization or death from any cause, the sample size was adjusted to approximately 1880 participants. This adjustment is expected to provide the required total number of 26 COVID-19-related hospitalizations or death from any cause, which will have approximately 90% conditional power (based on the second interim analysis data) such that the nominal 95% CI of the treatment group difference in the event rate does not include 0 when assuming that PF-07321332/ritonavir reduces the event rate by 70% or more relative to placebo.

The sample size increase of 740 participants is based on the assumption of a 1.5% event rate for the targeted enrollment countries. The number of participants is approximately 1880 (1140 enrolled participants plus the increase of 740 participants). Assuming a 5% premature study discontinuation rate, approximately 1980 participants will be enrolled in the study.

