6.2.2. Incidence of SAEs and AEs Leading to Discontinuations

The incidence of SAEs and AEs leading to discontinuation will be summarized by treatment group using the SAS population.

6.2.3. Proportion of Participants with COVID-19 Related Hospitalization or Death From Any Cause Through Day 28

The estimand for proportion of participants experiencing COVID-19 related hospitalization or death from any cause through Day 28 is the difference in proportions of participants experiencing COVID-19 related hospitalization or death from any cause through Day 28 in nonhospitalized adult patients with COVID-19 who are at low risk of progression to severe disease and were treated ≤ 5 days after COVID-19 symptom onset. This will be estimated irrespective of adherence to randomized treatment.

The statistical methodology for proportion of participants with COVID-19 related hospitalization or death from any cause through Day 28 will be as follows:

The cumulative proportion of participants hospitalized for the treatment of COVID-19 or death during the first 28 days of the study will be estimated for each treatment group using the Kaplan-Meier method to take account of lost to follow-up and summarized graphically for each treatment group. The estimand is the difference of the proportions in the 2 groups and its 95% CI will be presented, as well as, the associated two sample proportion test (Wald test results). For the 95% CI, the corresponding estimate of the standard error is computed using Greenwood's formula⁴. The Greenwood's formula to estimate the variance of the difference of proportions at Day 28 is $[\text{Var}(S_{PF}(28)) + \text{Var}(S_{\text{Placebo}}(28))]$. Instead of dealing with $S(t_i)$ the log-log approach to CI will be used. The 95% CI will be computed for the estimate of $L(t) = \log(-\log(S(t)))$, the log hazard function.

The CI will be in the right range when transformed back to $S(t) = \exp(-\exp(L(t)))$. Antilogging this CI will give a 95% confidence interval for the difference itself.

A sensitivity analysis for proportion of participants with COVID-19 related hospitalization or death from any cause through Day 28 will be provided using mITT1 as follows:

For participants with missing data due to lost to follow up for COVID-19 related hospitalization or death from any cause, the sensitivity analysis will implement the following event imputation methodology for those with missing data:

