9. APPENDICES

Appendix 1. Summary of Efficacy Analyses

Endpoint	Analysis Type	Population	Data Inclusion and Rules for Handling Intercurrent Events and Missing Data	Analysis Model
Time (days) to sustained alleviation of all targeted COVID-19 signs/symptoms through Day 28.	Primary efficacy Analysis	mITT1	All data collected will be included. Missing severity at baseline will be treated as mild. Other missing data will be estimated with KM (lifetest) procedure	Kaplan-Meier & Log rank test
Time (days) to sustained alleviation of all targeted COVID-19 signs/symptoms through Day 28.	Sensitivity analysis for primary endpoint	mITT1	All data collected will be included. Missing severity at baseline will be treated as mild.	Cox proportional hazard model
Time (days) to sustained alleviation of all targeted COVID-19 signs/symptoms through Day 28.	Sensitivity analysis for primary endpoint	mITT1 exclude site 1488	All data collected will be included. Missing severity at baseline will be treated as mild.	Cox proportional hazard model
Time (days) to sustained alleviation of all targeted COVID-19 signs/symptoms through Day 28.	Supplemental analysis for primary endpoint	PP	Participants who discontinued the study before Day 28 without event will be censored at Day 25.	Kaplan-Meier & Log rank test
Time (days) to sustained alleviation of all targeted COVID-19 signs/symptoms through Day 28.	Sensitivity analysis for Primary Efficacy analysis for multiple enrollers	mITT1 including only data with first randomization within the study	All data collected will be included regardless of intercurrent events. Kaplan-Meier method to take account of losses to follow-up.	Kaplan-Meier method
Time (days) to sustained alleviation of all targeted COVID-19 signs/symptoms through Day 28 by vaccination status	Subgroup analysis for primary endpoint	mITT1	Use baseline variables as described in Section 6.4.	Cox proportional hazard model
Proportion of participants with COVID-19 related hospitalization or death from any cause through Day 28	Key secondary analysis	mITT1	All data collected will be included regardless of intercurrent events. Kaplan-Meier method to take account of losses to follow-up.	Kaplan-Meier method

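### The 95% CI for the key secondary risk difference is specified in two ways, and the log-log version cannot produce an interval for a difference

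*SAP*

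**What the plan says.** SAP 6.2.3 and protocol 9.3.3 describe this analysis in nearly the same words. In the SAP, the target is clear: "The estimand is the difference of the proportions in the 2 groups and its 95% CI will be presented", with a Wald test beside it. The scale is then set: "For the 95% CI, the corresponding estimate of the standard error is computed using" Greenwood's formula, and the variance of the difference at Day 28 is Var(S_PF(28)) + Var(S_Placebo(28)).

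The next sentence, which opens with the word *instead*, changes course: "the log-log approach to CI will be used". The interval is to be computed for L(t) = log(-log S(t)) and transformed back by S(t) = exp(-exp(L(t))). The paragraph closes: "Antilogging this CI will give a 95% confidence interval for the difference itself". The protocol has the same closing sentence.

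SAP Appendix 1 does not settle the matter. For this endpoint it says "Kaplan-Meier method to take account of losses to follow-up", and its analysis-model column names only the Kaplan-Meier method.

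The interval has a stated use. Protocol 9.5 and SAP 2.3 size the extension on conditional power "such that the nominal 95% CI of the treatment group difference in the event rate does not include 0".

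**The concern.** The linear Greenwood variance is enough to build an interval for the difference, and it matches the Wald test. The log-log instruction that follows is written for a single survival function. Neither document defines L for a difference or says how the two arms' L values are to be combined, yet both say the outcome is an interval for the difference.

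An analyst following the text must therefore either ignore its last instruction or invent a step. This is the endpoint that drove the sample-size increase. Protocol 9.1 and SAP 5.1 make its point estimate and 95% CI the reported result. With about 26 events expected, the choice of scale can decide whether the printed interval includes 0, and a log-log-based interval need not agree with the Wald test printed next to it.

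**Working it through.** **Inputs.** First-interim counts from protocol 2.2.2: "2 of 333 hospitalized with no deaths" on drug and 8 of 329 on placebo. From protocol 9.5 and SAP 2.3: 26 events, a 70% reduction, and 1880 participants, hence 940 per arm at 1:1. I assume no censoring, so the Greenwood variance reduces to p(1-p)/n.

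**The plan's own figures.** 1140 + 740 = 1880, and 1880/0.95 = 1979, against the stated 1980. The 90% conditional power cannot be reproduced, because the second-interim counts are not given.

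**Step 1: the linear interval, 2/333 v 8/329.**
- Event proportions: 0.601% and 2.432%, so d = -1.831 points.
- Variances: 1.793e-5 and 7.211e-5. SE = sqrt(9.004e-5) = 0.949 points.
- d ± 1.96 × SE = **-3.69 to +0.03 points**, Wald p = 0.054.

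**Step 2: the log-log text taken literally, same counts.**
- SE(L) = sqrt(Var S)/(S·|log S|) = 0.707 on drug and 0.354 on placebo.
- exp(-exp(L ± 1.96·SE)) gives S(28) of 0.976 to 0.9985 on drug and 0.952 to 0.988 on placebo. These are two single-arm intervals.
- Differencing L, a step the text does not state: -5.112 - (-3.704) = -1.408, with SE = sqrt(0.707² + 0.354²) = 0.791 and interval -2.957 to 0.142. The antilog is 0.245 (0.052 to 1.152), a cumulative hazard ratio with null value 1.
- Applying exp(-exp()) to that contrast gives 0.783 (0.316 to 0.949). This form always lies strictly between 0 and 1, so it can never contain 0. With identical arms (13/940 each) it gives 0.368 (0.116 to 0.629), although the difference is exactly 0.

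None of these is an interval for -1.83 points.

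**Step 3: could the choice of scale change the result?** A valid interval for the difference can be built from the two arms' log-log limits by the MOVER method. With limits (l, u) on each arm's event proportion, the upper limit is d + sqrt((u1 - p1)² + (p0 - l0)²), and the lower limit is the mirror image. At 2/333 v 8/329 it gives -4.25 to +0.32 points. At 26 events and 940 per arm, upper limits in percentage points are:

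| Drug v placebo | Greenwood/Wald | MOVER | Antilogged ratio |
|---|---|---|---|
| 7 v 19 | -0.222 | -0.187 | 0.871 |
| 8 v 18 | -0.009 (p = 0.048) | +0.035 | 1.017 (p = 0.055) |
| 9 v 17 | +0.204 | +0.257 | 1.183 |

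At 8 v 18 only the linear interval excludes its null. Wald and MOVER disagree in the same way at 900 and at 990 per arm.

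**Step 4: how often?**
- Given 26 events, drug events ~ Binomial(26, RR/(1+RR)). P(exactly 8) = 0.112 at RR 0.3 and 0.161 at RR 0.5.
- Across totals of 20 to 33 at 940 per arm, Wald and MOVER disagree at only three totals, one split each: 6 v 15, 8 v 18 and 10 v 21.
- If the total is allowed to vary (independent binomials, mean 26 events), the probability of disagreement is 2.3% at a 70% reduction and 3.1% at 50%.
- Continuing from 2 v 8 with 16 more events at a 70% reduction, further drug events ~ Binomial(16, 0.3/1.3). The chance of excluding 0 is P(total ≤ 8) = 0.945 by Wald and P(total ≤ 7) = 0.858 by MOVER. This starts from first-interim counts, so it does not test the plan's 90%.

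**The case against.** The strongest reply is that the plan already holds a complete rule for the difference. L(t) and its back-transform are functions of one curve, so a sensible reader would use log-log limits for each arm's Kaplan-Meier estimate and the Greenwood variance for the difference. On that view only the closing sentence is wrong. This is the sensible reading, and the fix below adopts it. But the text does not say it: the log-log approach is introduced as a replacement, and the closing sentence claims the difference as its target.

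Second, MOVER appears in neither document, so the 8 v 18 reversal compares the plan's method with an outside one. That is correct. MOVER only shows what a valid log-log-based interval would do. The nearest literal reading, the antilogged ratio, also fails to exclude its null at 8 v 18, but nobody would report it as a risk difference.

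Third, 26 is an expected count and not a stopping rule, so the 11% and 16% overstate the exposure; 2.3% and 3.1% are the better overall figures. At the only counts the documents give, both intervals include 0. All of this stands and limits the size of the problem.

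Fourth, inference is nominal, and the point estimate, estimand and sample size are untouched. That also stands. It bears on how serious the error is, not on whether the instruction is wrong.

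**Conclusion.** The concern holds. The statement that antilogging the log-log interval gives an interval for the difference is mathematically wrong in both documents, and nothing elsewhere in them repairs it. The practical effect is limited: the two valid intervals disagree about 0 at one split of the planned 26 events and, with the total left free, in about 2% to 3% of trials at a 50% to 70% reduction. These figures assume no censoring, 940 per arm and MOVER as the log-log alternative.

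The error should still be corrected. The point estimate and interval are the planned result for the endpoint that justified the extension, and the method should not be left open until the data are in hand.

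**What to change.** In SAP 6.2.3, and in protocol 9.3.3 so that the two agree:

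- Delete the antilogging sentence.
- State one method: the 95% CI for the difference in Day 28 event proportions (drug minus placebo) is [S_Placebo(28) - S_PF(28)] ± 1.96 × sqrt(Var(S_PF(28)) + Var(S_Placebo(28))), with Greenwood variances, and the Wald test uses the same standard error. Another valid interval for a difference would also serve if it were named. This one uses the plan's own variance and agrees with its own test.
- Confine log(-log S(t)) to each arm's own interval.
- Name the CI method in the Appendix 1 rows for this endpoint.

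Two minor points can be handled in the same edit. The protocol prints log(log(S(t))) without the SAP's minus sign; this is clerical and may come from the PDF reading. It is also worth saying what is reported if a subgroup arm has no events, since the log-log form is then undefined.

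The cost is a few lines of wording. No new data are needed, and the estimand and sample size do not change.
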